4.4 Baseline Characteristics

The following baseline characteristics will be presented in mITT, PP and AT population:

- Sex, categorical variable;
- Age, continuous variable, measured in years;
- Body Mass Index, continuous variable, measured in kg/m²;
- American Society of Anesthesiologists grading, categorical variable
- Eastern Cooperative Oncology Group performance status score, categorical variable;
- Tumor site, categorical variable, classified as distal transverse colon (distal 1/2 of transverse colon), splenic flexure of colon (junction of transverse colon and descending colon), descending colon (descending colon and the junction of sigmoid colon and descending colon), and proximal sigmoid colon (proximal 1/3 of sigmoid colon);
- NRS2002 score, continuous variable, measured in points
- Parenteral prophylactic antibiotics, categorical variable;
- Mechanical bowel preparation, categorical variable;
- Oral antibiotic bowel preparation, categorical variable;
- Postoperative antibiotic use time, categorical variable, divide by ≥ 3 days and < 3 days;
- Clinical T stage, categorical variable;
- Clinical N stage, categorical variable;
- Clinical TNM stage, categorical variable;

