4.5 Primary endpoint

The primary endpoint in this trial is surgical site infection (SSI) within 30 postoperative days. Cases that fail to complete the 30-day follow-up are treated as missing data. The SSI will be compared between groups in the mITT population, PP population, and AT population.

- Overall SSI, Categorical variable. The absolute risk differences and the corresponding 95% CI between two groups will be calculated. The 95% CI will be compared with the non-inferiority margin (5%).

The subtypes of SSI (Superficial or deep incisional SSI, and Organ/space SSI) will also be compared between the two groups. However, their 95% confidence interval will not be compared with the non-inferiority margin.

The independent risk factors for overall surgical site infection (SSI) will be analyzed in the AT population. In univariable analysis, continuous variables will be converted to categorical variables. Chi-square tests or Fisher's exact tests will be employed. The key variables are as follows.

- Sex (male, female);
- Age (≤ 65 years, > 65 years);
- Body Mass Index ($\leq 24 \text{kg/m}^2$, $> 24 \text{kg/m}^2$);
- American Society of Anesthesiologists grading (I, II, III);
- Eastern Cooperative Oncology Group performance status score (0, 1, 2);
- Tumor site (distal transverse colon, splenic flexure of colon, descending colon, and proximal sigmoid colon);
- NRS2002 score (≤ 2 points, > 2 points);
- Parenteral prophylactic antibiotics (Yes, No);
- Mechanical bowel preparation (No, only enema, only oral laxative, enema plus oral laxative);
- Oral antibiotic bowel preparation (Yes, No);
- Postoperative antibiotic use time (≥ 3 days, < 3 days);

- Pathological TNM stage (0, I, II, III);
- Overflow of intestinal contents during anastomosis (Yes, No);
- Operating time (≤ 180 mins, > 180 mins);
- Blood loss during operation (≤ 100 ml, > 100 ml);
- Blood transfusion during operation (Yes, No);
- Prophylactic enterostomy (Yes, No);
- Anastomosis methods (Side-to-side anastomosis, End-to-side anastomosis, End-to-end anastomosis)
- Intervention (intracorporeal anastomosis, extracorporeal anastomosis)

Factors clinically relevant to SSI after univariable analysis will be included in multivariable analysis. Logistic regression will be used in multivariable analysis to identify independent risk factors for SSI. The effect size will be estimated using odds ratios (ORs) with 95% confidence intervals.

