4.6 Secondary endpoints

The secondary endpoints will be compared between groups in the mITT population, PP population, and AT population.

- Operating time, continuous variable, measured in minutes;
- Total blood loss during operation, continuous variable, measured in milliliters;
- Conversion to open surgery, categorical variable;
- Postoperative complications, categorical variable. It will be analyzed according to the overall occurrence. The occurrence of its subtype (anastomotic leakage, bowel obstruction, etc.) will also be analyzed. Additionally, Clavien–Dindo classification will be analyzed (\leq grade II, \geq grade III). (3)
- Completeness of specimens, categorical variable. It is evaluated according to the West classification (mesocolic plane, intramesocolic plane, and muscularis propria plane).(4)
- Number of lymph nodes dissected, continuous variable.
- The pathological TNM stage (as per the American Joint Committee on Cancer

Cancer Staging Manual, 8th edition), categorical variable. The T stage, N stage, and TNM stage will be analyzed separately.

- Postoperative recovery, continuous variable. It includes the time to first flatus, the time to first defecation, the time to start food intake, and the postoperative hospital stay. Additionally, the time to first ambulation and the time to remove the abdominal drainage tube, which are not included in the study protocol's design, will also be analyzed. These are measured in days.
- Length of incision, continuous variable. It is measured in millimeters.
- Visual analog score (VAS) of pain, it will be analyzed as categorical variable: no to mild pain (0–3 points); moderate pain (4–6 points), and severe pain (7–10 points).
- 3-year DFS: DFS is defined as the time from randomization until the occurrence of local recurrence, distant metastasis, or death from the tumor, whichever comes first. It is measured in months. For patients who are lost to follow-up, DFS will be censored at the time of the last available tumor assessment before the missing assessments.
- 5-year OS: OS was defined as the time from randomization to death due to any cause. It is measured in months. For patients lost to follow-up, OS will be censored at the time of the last available follow-up prior to the missing assessments.

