4.7 Subgroup analysis

The subgroup analysis will be carried out only if the primary endpoint in the mITT population do not reach the non-inferiority margin. If the 95% CI of SSI is not within the non-inferiority margin, the primary endpoint will be summarized within the following subgroups.

- Sex (male, female);
- Age (≤ 65 years, > 65 years);
- Body Mass Index ($\leq 24 \text{ kg/m}^2$, $> 24 \text{ kg/m}^2$);
- Tumor site (distal transverse colon or splenic flexure of colon, descending colon,

proximal sigmoid colon);

- NRS2002 score (≤ 2 points, > 2 points);
- Mechanical bowel preparation (Yes, No);
- Oral antibiotic bowel preparation (Yes, No);
- Postoperative antibiotic use time(≥ 3 days, < 3 days);
- Operating time (≤ 180 mins, > 180 mins);

Subgroup analyses will be performed using mITT population. If intracorporeal anastomosis is proven to be noninferior to extracorporeal anastomosis regarding SSI, subgroup analysis will not be performed.

5 Missing data

Missing primary endpoint data will be treated as censored data and won't be imputed during analysis. Other missing data won't be imputed either. The missing data will be stated in the tables.

6 Interim analyses

No interim analyses are planned in this study.

7 Timing of analysis

We will conduct an analysis of the study's primary endpoint and publish the relevant findings after enrollment is completed and all patients have completed the first month of follow-up after surgery. When all patients complete 5 years of follow-up, the results involving survival data will be analyzed again, and the relevant research results will be published.

Reference

1. He L, Li M, Zhang J xin, Tong W hua, Chen Y, Wang Q. Surgical site infection after intracorporeal anastomosis for left-sided colon cancer: study protocol for a non-

inferiority multicenter randomized controlled trial (STARS). *Trials*. 2022 Nov 22;23(1):954.

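### SAP 4.7 splits the SSI comparison by postoperative antibiotic time and operating time, which arise during or after the randomised operation; antibiotic time can also be a consequence of SSI

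*Combined protocol and SAP*

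**What the plan says.** SAP 4.7 is conditional: "The subgroup analysis will be carried out only if the primary endpoint in the mITT population do not reach the non-inferiority margin". In that case "the primary endpoint will be summarized within the following subgroups", in the mITT population. Nine factors follow. Seven are sex, age, BMI, tumour site, NRS2002 score, mechanical bowel preparation and oral antibiotic bowel preparation. The other two are "Postoperative antibiotic use time(≥ 3 days, < 3 days") and "Operating time (≤ 180 mins, > 180 mins").

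The same two variables appear elsewhere:

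- **SAP 4.4**, under baseline characteristics: "Postoperative antibiotic use time, categorical variable", split at 3 days.
- **SAP 4.5**, among the candidate SSI risk factors in the as-treated population: "Postoperative antibiotic use time (≥ 3 days, < 3 days"). The step to the multivariable model is: "Factors clinically relevant to SSI after univariable analysis will be included in multivariable analysis".
- **SAP 4.6**, first secondary endpoint: "Operating time, continuous variable, measured in minutes". Protocol v2.1 section 3.2.2 measures it from skin incision to skin closure or enterostomy.

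For timing, protocol v2.1 section 7.4 aims to randomise on the day before surgery. Section 7.1 describes preoperative antibiotics only. No section defines postoperative antibiotic use time, limits it to prophylaxis, or stops the count at SSI onset. Attachment 4 puts incisional infections that need antibiotics in Clavien-Dindo grade II. Section 6.2 says that surgeons know the allocation.

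**The concern.** A subgroup comparison keeps the protection of randomisation only if subgroup membership cannot be changed by the treatment or by the outcome. Neither variable meets that condition. Operating time is measured on the randomised operation itself, and the SAP treats it as an outcome of that operation. Antibiotic time accrues during the 30-day window in which SSI is counted. As the text stands, treating an SSI can move a patient into the longer-course stratum, so the endpoint helps to decide who is in the stratum.

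Three exploratory outputs are exposed:

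- **Subgroup table:** it can show a treatment difference, or a difference between strata, that the definition of the strata created.
- **Risk-factor analysis:** it can report antibiotic time as a risk factor when SSI caused the longer course.
- **Baseline table:** it presents a postoperative variable as if it described the arms before treatment.

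The subgroup table is produced only after non-inferiority has not been shown, when readers will be looking for an explanation. The other two outputs are unconditional.

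**Working it through.** **1. The plan's own figure.** SAP section 3 gives EA 13.3%, IA 8.0%, margin 5 points, one-sided 0.025, power 0.80 and 20% drop-out.

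n per arm = (1.960 + 0.842)² × (0.133×0.867 + 0.080×0.920) / (0.05 + 0.053)² = 7.849 × 0.1889 / 0.01061 = 139.8, so 140.

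140/0.8 = 175 per arm, 350 in total. The stated size reproduces, and nothing below changes it.

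**2. Antibiotic strata with no IA effect.** Let p be the SSI risk, s the share of SSI patients with at least 3 days, and u the share of non-SSI patients with at least 3 days. Then:

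- SSI risk in the ≥3-day stratum = ps / [ps + (1−p)u]
- SSI risk in the <3-day stratum = p(1−s) / [p(1−s) + (1−p)(1−u)]

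Only p = 0.133 comes from the documents (the EA planning rate, used here in both arms). The values of s and u are assumptions. With s = 0.9 and u = 0.5, the ≥3-day risk is 0.1197/(0.1197 + 0.4335) = 21.6% and the <3-day risk is 0.0133/(0.0133 + 0.4335) = 3.0%. Other values of u follow in the same way.

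| u in EA / IA | ≥3 days, IA − EA | <3 days, IA − EA |
|---|---|---|
| 50% / 50% | 0 | 0 |
| 50% / 40% | 25.7 − 21.6 = +4.0 | −0.5 |
| 50% / 30% | 31.5 − 21.6 = +9.9 | −0.8 |
| 80% / 80% | 0 | 0 |
| 80% / 70% | 16.5 − 14.7 = +1.8 | −2.3 |
| 80% / 60% | 18.7 − 14.7 = +4.0 | −3.4 |

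(Differences are taken before rounding.) The signs reverse if IA patients have the longer courses. With s from 0.70 to 0.95, the 50%/40% row gives +3.5 to +4.1 and −1.3 to −0.3.

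**3. False signals in the ≥3-day stratum.** Simulated trials with no IA effect, 140 and 175 per arm, Wald 95% CI:

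| Non-SSI use with IA | CI excludes 0 |
|---|---|
| Equal to EA | about 5% |
| 10 points lower | 9–10% (50/40); 6.5–7% (80/70) |
| 20 points lower | 24–29% (50/30); 11–13% (80/60) |

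These rates are not conditioned on the 4.7 trigger. Among trials that miss non-inferiority they rise to about 11–13% for 50/40 and 31–40% for 50/30. The CI half-width in this stratum is about 12 to 15 points in the 50% cases.

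**4. A real IA effect with equal use by arm.** Take s = 0.9 and u = 0.5 in both arms.

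- Overall +5.0 points (18.3% against 13.3%): ≥3 days 28.7 − 21.6 = +7.1; <3 days 4.3 − 3.0 = +1.3.
- Planning effect −5.3 points: ≥3 days 13.5 − 21.6 = −8.1; <3 days 1.7 − 3.0 = −1.3.

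The stratum odds are [p/(1−p)] × s/u, or the same with (1−s)/(1−u), so the odds ratio is the same in both strata (1.46 in the +5.0 case). The apparent modification is on the risk-difference scale, which is the scale the SAP uses for SSI.

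**5. Risk-factor analysis.** With no causal effect of antibiotic time, its odds ratio is [s/(1−s)] / [u/(1−u)]. With s = 0.9 this is 9/1 = 9 for u = 0.5 and 9/4 = 2.25 for u = 0.8.

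**6. Operating time.** Assume 40% difficult cases with SSI 21.25% and 60% easy cases with 8% (0.4×21.25 + 0.6×8 = 13.3%), no IA effect, and an operation over 180 minutes in 30% (easy) and 80% (difficult) with IA against 10% and 50% with EA.

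- ≤180 min: IA (0.42×8 + 0.08×21.25)/0.50 = 10.1%; EA (0.54×8 + 0.20×21.25)/0.74 = 11.6%; difference −1.5.
- >180 min: IA (0.18×8 + 0.32×21.25)/0.50 = 16.5%; EA (0.06×8 + 0.20×21.25)/0.26 = 18.2%; difference −1.7.

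The two strata shift by similar amounts.

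**7. How often the tables appear.** Simulated with 140 to 175 per arm, non-inferiority is missed in 12–19% of trials at the planning rates and in 72–76% if both rates are 13.3%.

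**The case against.** The strongest reply is that the reach is small. The primary comparison is unadjusted and untouched. The subgroups are conditional, and 4.7 only summarises: it plans no interaction test and no comparison with the margin within subgroups. All of this stands, and it confines the point to exploratory tables. It does not justify stratifiers that the outcome can determine.

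Second, with no IA effect the artefact is exactly zero unless antibiotic use differs by arm. A reader might infer from the unblinded surgeons that use does differ. The documents do not say so, and the +9.9 needs a 20-point imbalance for which they give no evidence. That also stands. Equal use removes the artefact only when IA has no effect (step 4).

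Third, a reader might infer that SSI-treatment days are counted. The SAP does not say that; it leaves the variable undefined, and Attachment 4 is a grading table. The supported statement is that nothing excludes those days.

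Fourth, a reader might extend the point to the two bowel-preparation factors, since both could follow a day-before randomisation. They precede surgery and SSI, so neither can alter them. The test for a subgroup factor here is whether the operation or the outcome can affect it.

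Fifth, a reader might infer that the 4.5 model offers its adjusted IA odds ratio as the effect of IA. The SAP presents that model as a search for risk factors and estimates the IA comparison as an unadjusted risk difference.

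Finally, labelling the two subgroups as non-randomised descriptive summaries would reduce the harm. It would leave the outcome-dependent stratum in place.

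**Conclusion.** The point holds for the exploratory analyses. SAP 4.7 uses two stratifiers that arise during or after the randomised operation. One of them, as written, can be a consequence of SSI and is also misplaced as a baseline characteristic and as a candidate risk factor.

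The sizes are illustrative: only the planning rates, margin and sample size come from the documents. At 13.3% SSI in both arms and s = 0.9, the spurious ≥3-day difference is 0 with equal use, +1.8 to +4.0 points with a 10-point imbalance, and +4.0 to +9.9 with a 20-point imbalance. The corresponding chances of a false signal are about 5%, 6.5–10% and 11–29% before conditioning on the trigger. With equal use, an overall +5.0 appears as about +7.1 and +1.3. The operating-time artefact is smaller and is mainly a common shift.

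The documents do not support a conclusion that the primary result, its error rate or N=350 is compromised.

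**What to change.** - **SAP 4.7:** delete postoperative antibiotic use time and operating time. Keep the seven factors that neither the operation nor SSI can affect, including the two bowel-preparation factors, which precede surgery.
- **SAP 4.4:** move postoperative antibiotic use time to a postoperative table, and state whether days given to treat an SSI count.
- **SAP 4.5:** drop it from the SSI risk-factor analysis. Recoding it as use before SSI onset is not a substitute, because early SSIs would then fall in the <3-day group automatically.

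These are text edits and need no new data. The cost is two fewer exploratory subgroups and one fewer candidate risk factor.
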